#### [System set-up and application](#)

All participants will receive a smartphone pre-loaded with apps associated with elements of the study program. These apps include the Dexcom CGM system app, the Fitbit app, and the Glucose Guide app created for this program to support patient coaching and research (e.g. texting). In addition, the Dexcom transmitter will be paired to the Dexcom app for each patient. Each of these steps by staff--app pre-loading, pre-registration and device pairing--will reduce the patient burden and allow program participants to begin the program by focusing on the fundamentals of using their devices.

Patients who choose to start using their CGM systems at home on their own will be asked to first review the instructional materials and videos. Patients who receive their devices during a group visit will be provided with information and instruction when they attend the visit.

Program resources and instructions will be accessible to patients in written form, in person, via telephone, and via video to help them with device application and system usage.

Prior to releasing program devices to patients, we will conduct user testing with the investigational CGM and other study devices. Select study staff and employees of the Sponsor will apply the investigational CGM and ensure that all device communications and app displays are working as intended. Devices will also be used by study coaches, representatives, and other staff as part of their training for the study. Testing will focus on verifying operational reliability, and training will focus on developing an understanding of the devices. Users will complete an informed consent form specifically for these purposes prior to using the investigational devices. We estimate needing devices to equip approximately 35 study staff.

Study staff will also evaluate the potential use alternative devices that may improve the participant experience. This may include the Fitbit Ionic smartwatch, which uses investigational software to provide a secondary display of the participant's estimated glucose value (EGV), the time since the last sensor reading, and arrows to indicate the EGV rate of change, mirroring information displayed by the Dexcom investigational CGM system app.

#### [CGM-based education and coaching](#)

This part of the study will be implemented by coaches who have undergone diabetes management training that incorporates device information, educational content, and techniques based on behavioral discussion and patient self-learning/empowerment. Coaches will also be equipped to help patients use

activity data in conjunction with their CGM use. Coaches will receive training regarding human research subjects to insure the ethical treatment and safety of all participants. All training will be reinforced during contact with study staff.

The information contained in the Standard of Care document has been approved by the study's Medical Directors (co-investigators) as providing fundamental diabetes self-management information to patients with T2D. In the Standard of Care document, patients are instructed that this information does not replace individual guidance given to patients from their providers.

Each participant will be assigned a coach who will provide education and support via phone and secure text messaging throughout the course of the study. Education will be centered around the four educational objectives (food intake and PPG, walking to reduce PPG, medication adherence, and nighttime glucose monitoring) and reinforcement of messages in the patient standard of care document. The coach will provide education on how to optimally use the CGM system for self-discovery, focusing on effective times to look at the CGM and behaviors that are likely to impact the CGM (outlined above). Coaches will assist participants in setting personalized goals and act as a sounding board for participants to discuss their self-discoveries. Coaches will review with patients the Rule of 15 to deal with hypoglycemic episodes.

#### [Integration with patient care](#)

Throughout the program, patients will be instructed to follow their normal care plan as directed by their medical providers and as consistent with ADA 2017 standard-of-care guidelines. This includes taking medications as prescribed; engaging in physical activity—especially walking after meals; eating a diet that optimizes glucose control through food choice and timing; responding to hypoglycemia symptoms with a fingerstick and consuming a pre-determined amount of glucose; and monitoring emotional wellness. By providing a continuous graph of each participant's glucose, the CGM system illustrates how the above-described glucose management behaviors impact the participant's glucose.

Should patients in the course of the program experience any health problems associated with the use of their CGM devices, they will be directed to contact the study doctor's CRC. The CRC will assess the severity and relatedness of the event and arrange for appropriate care. Should patients mention a potential study-related health concern to their coach, the coach will actively work to assure the patient speaks with the study doctor, either through a warm transfer or callback.

#### [Program devices](#)

##### [Dexcom CGM System](#)

Patients in this study will employ an investigational-use only (IUS) CGM system manufactured by Dexcom, Inc. (San Diego, CA). The devices in this system (a sensor with auto-applicator, a transmitter, and a mobile application) represent a variation of the Dexcom G6 CGM system which received approval by the FDA under an investigational device exemption (IDE) on April 28, 2016. The ways in which these study devices vary from the G6 system and the commercial G5 system are described here as well as in the attached Investigator's Brochure.

The investigational system represents several improvements over the commercially-available Dexcom CGM systems. The investigational applicator is designed to improve ease of use and reduce the risk of user error compared to Dexcom's G5 commercial device by simplifying the application process. While

the commercial device requires the user to perform multiple actions to deploy the sensor-delivery needle, retract the needle, and release the applicator from the transmitter holder, the investigational applicator performs all of these steps with just one action by the user.

The investigational sensor has a lifetime of 10 days, as opposed to the 7-day lifetime of Dexcom's commercial G5 sensor. As a result, users will not need to change their sensors as often, further reducing risk for any difficulties or inconvenience associated with sensor application. The sensor has also been redesigned to reduce sensor error associated with the use of acetaminophen, thus improving the reliability of sensor readings.

Compared to the Dexcom G6 transmitter, the IUO transmitter has a lower design profile to improve everyday wearability.

The mobile (smartphone) app displays glucose information in real-time. To maintain the accuracy of these readings, the system must be calibrated periodically based on fingerstick readings from a blood glucose meter. After initial calibrations, the investigational app requires less frequent calibrations than the commercial device. While the commercial system requires calibration every 12 hours, after the first day the investigational system requires calibration every 24 hours. This improvement is expected to further improve the usability and acceptance of the CGM system.

During CGM wear, a sterile disposable glucose sensor is applied on the abdomen and held in place with an adhesive. The wire-like sensor is not significantly thicker than the needles used in syringes for insulin injection. The needle insertion depth ranges from 0.35 – 0.55 inches.

Once in place, the sensor pod consists of a glucose oxidase-based electrochemical sensor placed subcutaneously to measure interstitial glucose concentrations over a 40-400 mg/dL range. The transmitter attached to the sensor pod will wirelessly send the sensor's glucose measurements via Bluetooth to a smartphone for display of trends and continuous glucose readings every 5 minutes. Readings will also be stored in the cloud. In using cloud storage, the smartphone also permits protected sharing of data with coaches and other authorized study staff. The smartphone also provides a more user-friendly interface, including larger text. Alerts, alarms, and reminders will be set to minimize disruption for the patient while still supporting proper use of the device and allowing for patient customization.

Participants will need to calibrate their CGM systems using a commercially available blood-glucose meter per manufacturer instructions.

As part of the system's instructions for use, users are informed of the following:

- The system does not replace blood glucose measurements.
- Blood glucose values may differ from sensor glucose readings and the value from the blood glucose meter should be used for treatment decisions.
- Symptoms of high and low glucose should not be ignored. If sensor readings do not fit with symptoms, blood glucose should be measured with a blood glucose meter.

Upon completion of 10 weeks of CGM use, patients will be asked to return their CGM transmitters and unused sensors. Patients will be allowed to keep their smartphones and activity trackers as long as they continue to sync the tracker at least every three weeks through the end of the study.

#### **Blood-Glucose Meter**

An over-the-counter blood-glucose meter will be used to approximate levels of glucose in the blood to calibrate the Dexcom CGM System. The battery-powered blood glucose meter will consist of an on/off switch, a display, and an opening for test strips. Patients are expected to already own their own blood glucose meters as part of their normal standard-of-care. Patients who do not have a glucose meter will be provided one to use and keep following the study.

#### **Activity Tracker System**

To help patients observe how physical activity impacts glucose levels, patients will be provided with a Fitbit Charge 2 wrist-worn activity tracker. This activity tracker will display in real-time the cumulative number of steps taken by the patient each day. The patient will also be able to view his/her step history via an app on the smartphone. The Fitbit activity tracker system consists of an activity tracker, a compatible charging cable, and an associated smartphone app that syncs step data to the Cloud.

Patients will be offered the option to use the activity tracker once they understand and are comfortable using their CGM systems and are ready to learn about physical activity.

Per protocol, patients will be asked to use their activity trackers through February 28, 2018. If patients sync their tracker data at least once every three weeks from the time they start using the activity tracker through February 28, 2018, then patients will be allowed to keep their activity tracker and smartphone. The data plan used during the study to sync data from devices will be terminated at the end of the study or when patients withdraw, which ever comes first.

#### **Training of site staff**

Site staff at Machuca Family Medicine will be oriented to the study and equipped to conduct recruitment and enrollment as needed. The CRC at the study site has previous experience in conducting clinical research specifically with Dexcom CGM devices. The CRC will be trained to instruct patients in using the investigational device. The CRC will also be trained in the specific protocol to assess and document adverse events.

## **7. Selection and Withdrawal of Subjects**

Study participants will be recruited from the Machuca Family Medicine patient census. To be eligible for the program, patients must meet specific inclusion/exclusion criteria. The criteria selects in particular for patients who struggle the most in managing their diabetes, as indicated by their diabetes medication(s). All patients who meet the selection criteria will be invited to participate in the program regardless of their latest A1C test.

---

 The Fitbit may also record and display distance walked, calories burned, active minutes, hourly activity, stationary time, heart rate, and sleep stages, duration, and consistency; and contain tools to help users meet their personal health and fitness goals.

We intend to enroll 100 program participants (defined as those to whom program materials and devices have been delivered). When 100 participants have been enrolled, any patients that have been recruited but who have not yet been enrolled (including those who may have signed a consent form) may choose to be notified of any other upcoming study opportunities for which they may be eligible.

### Inclusion Criteria

To be included in the study, patients must:

- Be diagnosed with type 2 diabetes
- Be able to read, speak, and understand English
- Have access to a telephone

### Exclusion Criteria

Patients will not be eligible if any of the following criteria pertain to them:

- Pregnant
- Blind
- Deaf
- Currently receiving chemotherapy or radiation therapy to treat cancer
- Addicted to any drugs (including alcohol, painkillers, hallucinogens, or others)
- Critically ill
- Diagnosed with or experiencing:
  - Kidney disease stages 4 and 5
  - End stage renal disease
  - Severe liver disease
  - Dementia
  - Schizophrenia
  - Bipolar disorder
  - Autism
  - An intellectual or learning disability
  - Arrhythmias other than atrial fibrillation
  - Congestive heart failure
- Has had a:
  - Myocardial infarction within the last 6 months
  - Stroke within the last 6 months
  - Stroke that resulted in significant disability (e.g., unable to write clearly or walk)

To ensure the medical records used to select patients accurately reflect the patient's current health status, patients will confirm their eligibility by reviewing the criteria provided in the consent packet and the consent form, and attesting to their eligibility by signing the consent form.

If during the study a patient's status changes such that s/he is no longer eligible to participate (with the exception of medication changes), the patient will be removed from the study. At that time the patient

will be asked to return all devices (with the exception of used sensors, the used transmitter, and the glucometer if the patient received one).

### Patient Participation

All program participants will participate at-will and have the freedom to terminate their participation at any time. Participants, including those who intend to withdraw from the program or those who have withdrawn will be able to access program coaches for assistance with any program-related questions or issues.

Coaches will schedule weekly calls with participating patients. If patients demonstrate by their actions that they no longer want to participate in the study by no longer syncing their CGM or activity tracker data, outbound call or text messaging efforts will be made to reach the patient. If after three weeks there has been no data received and no communication with the patient, a voicemail will be left asking patients to reply within three days or they will be considered dropped from the study. No response to these voicemails will result in the shipment to these patients of a postage-paid box and a letter. The letter will inform patients that they are considered as non-participating and need to return the CGM devices, activity tracker, and smartphone.

During the course of the program, should any participant report medical issues that may affect that patient's ability to participate in the program, the patient will be directed to consult with the study doctor.

## 8. Treatment of Subjects

This program will provide dedicated resources to assure informed consent.

Patients will be instructed to continue to follow the advice of their physicians, including taking prescribed medications.

Patients will sign and date an IRB-approved consent form that indicates that if they are injured from applying or wearing the CGM system or activity tracker in the course of the program that they will receive treatment and that their insurance may be billed. Copays and costs related to injuries from applying or wearing the CGM devices and activity tracker which are not paid for by patient's insurance will be covered by Savvysherpa (Sponsor). Charges for medical care will be based on insurance contracted rates and not mastercharge sheet prices.

Patients with medical concerns related to the study devices will be instructed to contact the study doctor and/or his staff for evaluation. Patients with any other health will be encouraged to see their providers, or if needed, seek emergency assistance as part of their normal standard of care.

Patients and study staff will be provided with the device manufacturers' technical assistance telephone numbers to report any device-related problems or concerns.

Patients will be provided with a program phone number to call and report other problems or concerns.

## 9. Assessment of Safety

While the proposed program is essentially educational in nature, every effort will be made to ensure that patients are using their devices properly. Should any concerns about patient safety arise, patients will be directed to see the study doctor or his staff, and if necessary, seek emergency medical assistance.

The Dexcom Continuous Glucose Monitoring System described in this protocol is considered by the Sponsor to be of non-significant risk as it does not meet the definition of a significant risk device per 21 CFR 812.3(m), in that CGM

- (1) Is not intended as an implant and presents a potential for serious risk to the health, safety, or welfare of a subject;
- (2) Is not purported or represented to be for a use in supporting or sustaining human life and presents a potential for serious risk to the health, safety, or welfare of a subject;
- (3) Is not for a use of substantial importance in diagnosing, curing, mitigating, or treating disease, or otherwise preventing impairment of human health and presents a potential for serious risk to the health, safety, or welfare of a subject; or
- (4) Otherwise does not present a potential for serious risk to the health, safety, or welfare of a subject.

Additionally, the system is being used in a manner not entailing significant risk, in that it is being used for educational purposes and as an adjunct to normal care.

The following information supports a non-significant risk determination for the device that will be used in this protocol:

- FDA-approved Dexcom CGM Systems have been considered a non-significant risk device;
- The CGM devices used in this study are being used on-label in the intended population;
- The Medtronic-Minimed Guardian RT® CGMS, an FDA-approved device using similar technology, has been considered a non-significant risk device;
- The FreeStyle Navigator® CGMS, an FDA-approved device using similar technology, has been considered a non-significant risk device;
- The insertion needle thickness used in the device is not significantly thicker than the needles used in syringes for insulin injection and the potential needle insertion depth is less than 0.6 inches;
- None of the expected device-related adverse events as defined in the protocol and associated documents would be life-threatening or would result in any permanent impairment of a body function or permanent damage to a body structure;
- There are no expected electrical safety risks as the device has passed the electrical safety tests as per EN45502-1 and EN60601;

- If the subject feels any discomfort during the course of the study, he/she will be able to remove the device immediately (the device is not permanent);
- The device is being used to complement, not replace, self-monitoring of blood glucose meter information, and readings are not intended to be used alone to make diabetes self-management decisions. As with the currently approved device and per intended use of similar technologies, subjects in the study will be instructed not to use the device for diabetes therapy or management;
- Subjects will be instructed to monitor their blood glucose levels as per their usual practice.

Adverse events (AE) associated with the use of the device include pruritus (severe itchiness present 48 hours after removal), erythema (reddening of the skin present 48 hours after removal), and inflammation (swelling and pain, defined as 8 or greater on a 10 point scale 48 hours after removal) where the adhesive touches the skin; local infection at insertion site; and shooting pain located at the site of the sensor (defined as 8 or greater on a 10 point scale). Rarely, the sensor wire will fracture when the sensor is being inserted, worn, or removed. If a sensor breaks and no portion of it is visible above the skin, the participant will be instructed to not remove it and seek medical care from the study doctor and/or his staff.

No serious adverse events (SAE) are expected as a result of participation in this minimal risk study. However, AE and SAE will be monitored in the following ways:

- Participants in the study will be instructed to call the study doctor's clinical research coordinator to report all AE and SAE related to the use of the study devices. The study doctor and/or his staff will assess the severity of any health problems associated with the device, and if needed, see the patient at the study clinic to assure appropriate care.
- Study coaches will listen for any reports of AE or SAE in the course of their communications with participants, and will connect reporting patients with the study doctor's clinical research coordinator so events can be assessed and documented and patients can receive care, if needed.
- Any reports of AE or SAE received by Dexcom's Customer Care and Technical Support representatives will be documented and reported to the Sponsor. Coaches will then promptly notify the study doctor's clinical research coordinator of these reports so that the coordinator can then follow up with the patient to assess event severity and relatedness, and schedule the patient for care, if needed.

The Sponsor-Investigator will receive CGM-related AE and SAE information from Dexcom through secure data transfers. AE and SAE information from the study doctor will also be stored and transferred securely. Any other records pertaining to AE and SAE from patient conversations with program staff will be recorded and documented using call-management software and the patient's Case Report Form.

The Sponsor-Investigator will ensure proper reporting of AE and SAE to Chesapeake IRB, the CGM manufacturer, the FDA, and any other regulatory bodies according to regulations and standard operating procedures. (See Appendix C for a chart illustrating the reporting process, and Appendix D for AE assessment guidance for coaches.)

Patients will be provided with a summary printout of their recorded CGM data at the end of their participation with CGM. Patients can share their CGM data with their providers.

The Standard of Care guidelines associated with the program direct patients to seek medical care when needed. Guidance exists within the guidelines to seek medical advice when glucose values are extremely high over long periods of time, fluctuate rapidly from high levels to low levels and vice versa, or a pattern of low glucose values is present. Coaches will remind patients of these guidelines but will not give medical advice. Coaches can send summary CGM data to patients upon patient request.

Because the CGM data is an adjunct to patients' diabetes care, the investigator and research staff will NOT constantly monitor patients' realtime CGM data nor will research staff and coaches contact patients' medical providers on behalf of patients when low or high CGM values are observed. Patients will be responsible for using the blood glucose meter to manage their diabetes and to seek medical attention when needed.

Episodes of hyperglycemia or hypoglycemia that require patients to seek medical attention will be considered an AE or SAE depending upon the situation.

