#### **Insertion Site Pain or Discomfort – Severity Category**

1. On a scale of 1 to 10, where 1 is very little, and 10 is severe, how much does your pain or discomfort affect your ability to do your daily activities?
  - If 1-2, do not record as AE
  - If 3-5, Mild AE
  - If 6-8, Moderate AE**
  - If 9-10, Severe AE**

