### Insertion Site Swelling – Severity Category

1. On a scale of 1 to 10, where 1 is very little, and 10 is severe, how would you rate the amount of swelling?
  - If 1-5, do not record as AE
  - If 6-7, Mild AE
  - If 8-9, Moderate AE
  - If 10, Severe AE

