### Insertion Site Swelling – Relatedness Category

1. Where is the location of the swelling?
  - If in the same location as the sensor on your skin, then Probably Related
  - If in a location where a sensor was within 2 days, then Possibly Related
  - If in a location where a sensor was 2+ days in the past, then Probably Not Related
  - If in a location where a sensor was never placed, then Not Related

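### Section 9 and the Appendix B coach scripts set inconsistent recording and relatedness rules for overlapping device skin and site events, and nothing shown says which governs

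*Protocol*

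**What the plan says.** Section 9 (Assessment of Safety) introduces its list with "Adverse events (AE) associated with the use of the device include pruritus (severe itchiness present 48 hours after removal". It goes on to erythema, qualified only by being present 48 hours after removal, and to "inflammation (swelling and pain, defined as 8 or greater on a 10 point scale 48 hours after removal", both at the adhesive contact area. Local infection follows, and then "shooting pain located at the site of the sensor (defined as 8 or greater on a 10 point scale". The shooting-pain item has a score but no time condition; the erythema item has a time condition but no score.

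Appendix B (Section 22) holds the questions coaches use to grade a complaint and document it.

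- Insertion-site pain or discomfort: "If 1-2, do not record as AE", then Mild at 3–5, Moderate at 6–8 and Severe at 9–10. The item asks "how much does your pain or discomfort affect your ability to do your daily activities".
- Pain accompanying redness or rash: the same bands, but the item rates the pain itself.
- Swelling: "If 1-5, do not record as AE", then Mild at 6–7, Moderate at 8–9 and Severe at 10.
- Redness or rash: recorded from 6; at 1–5 it is not recorded unless itchiness or pain is moderate.

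No severity question in these scripts refers to 48 hours after removal. Time enters only through the relatedness scripts, for example "If in a location where a sensor was 2+ days in the past, then Probably Not Related".

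**The concern.** Both texts decide whether a skin or site complaint is an adverse event, and they decide it differently. Section 9 attaches definitions to the events it names. Appendix B labels lower scores as Mild adverse events, so its bands are not merely a grading within the Section 9 definition. The relatedness rule also pulls against Section 9: persistence at 48 hours is part of what makes a sign a listed device event there, yet a site where the sensor was 2 or more days ago counts against the device in the script.

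What is at stake is the consistency of the safety record for an investigational device. Coaches are a first-line contact. They score severity and relatedness before any transfer to the clinic, and a complaint scripted as not recordable may go no further. A later analysis plan can choose a counting rule, but it cannot recover an answer that was never asked for or kept.

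**Working it through.** The protocol states no adverse event rate to reproduce, so the check applies each rule to every whole score from 1 to 10. The inputs are the cut-offs in Section 9 and in three Appendix B severity scripts (redness or rash, swelling, insertion-site pain).

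| Score | Section 9 score cut (inflammation, shooting pain) | Appendix B, pain with redness or rash | Appendix B, swelling |
|---|---|---|---|
| 1–2 | not met | not recorded | not recorded |
| 3–5 | not met | Mild | not recorded |
| 6–7 | not met | Moderate | Mild |
| 8 | met | Moderate | Moderate |
| 9 | met | Severe | Moderate |
| 10 | met | Severe | Severe |

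**Score alone, with any 48-hour condition taken as met**

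- Pain with redness or rash: Appendix B records 3–10 (8 scores) and Section 9 takes 8–10 (3 scores). They disagree at 3, 4, 5, 6 and 7: 8 − 3 = 5 of 10.
- Swelling: Appendix B records 6–10 (5 scores) and Section 9 takes 8–10 (3 scores). They disagree at 6 and 7: 5 − 3 = 2 of 10.
- Insertion-site pain: also recorded from 3, but no subtraction is made. That item scores interference with activities, and Section 9 does not say what its pain scale rates.

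**Timing.** Swelling that is rated while the sensor is worn, or that clears within 48 hours of removal, does not meet the Section 9 inflammation definition at any score. Appendix B records it at all 5 scores from 6 to 10.

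**The opposite direction.** Erythema present at 48 hours meets Section 9 at any score. Appendix B records redness at 6–10. At 1–5 (5 of 10 scores) it does not, unless itchiness or pain is moderate.

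**Relatedness.** The scripts give Probably Related for the current sensor site, Possibly Related for a site used within 2 days, and Probably Not Related from 2 days on. A sign persisting past 48 hours meets the Section 9 timing condition and falls in the last category.

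Three illustrative complaints show the effect:

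1. Swelling 7, sensor still on. Appendix B: Mild, Probably Related. Section 9 inflammation: not met on score or timing.
2. Redness 4, no itch or pain, still present three days after removal. Section 9: listed erythema. Appendix B: not recorded; relatedness would be Probably Not Related.
3. Swelling and pain both 9, three days after removal. Both texts make it an event. Section 9 lists it as device-associated; the swelling script grades it Probably Not Related.

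**The case against.** Several points on the other side are sound and limit what can be claimed.

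- A reader might infer that Section 9 counts pain or swelling only from 8. The list is introduced with the word include, so it is not stated to be exhaustive, and scores below 8 are not declared non-events. The events it names do carry their own definitions, however, and those do not match the scripts.
- The sites overlap rather than coincide. Section 9 inflammation is at the adhesive contact area and its other pain item is shooting pain at the sensor, while the scripts cover insertion-site signs and redness or rash generally.
- Appendix B does not ignore time. Its relatedness scripts split at about 2 days, and coaches are to document the answers given. Part of a reclassification may therefore be possible from planned data, and it would be too strong to say that the record could not be interpreted.
- A reader might infer that the event rate depends simply on who takes the call. Section 9 brings participants' own calls, coaches' referrals and the manufacturer's reports to the clinical research coordinator for assessment. What remains is the coach's prior grading and the absence of a stated rule for the coordinator.
- A reader might infer that reports to the IRB, manufacturer or FDA turn on these cut-offs. Section 9 ties that reporting to regulations and standard operating procedures, not to a score of 8.
- The study is a single-group formative evaluation with no planned comparison of event rates.
- Some material is not shown. Section 9 refers to "Appendix D for AE assessment guidance for coaches", whereas the coach questions available stand in Appendix B; the Appendix C chart and the complaints guidebook are also unseen. One of these may reconcile the rules, and their absence is not held against the plan.

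None of this removes the mismatch between the two texts at hand, including the part where Appendix B is the narrower rule.

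**Conclusion.** The inconsistency holds and should be corrected, although it does not touch the study's primary aim. Section 9 and Appendix B can classify the same complaint differently, and neither is simply the wider net. Appendix B takes in lower pain and swelling scores and signs during wear; Section 9 takes in mild redness that persists; and the two point in opposite directions on relatedness once 48 hours have passed.

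The size can be stated only in scale points: 5 of 10 for pain with redness or rash, 2 of 10 for swelling when the 48-hour condition is met, and 5 of 10 in the reverse direction for persistent redness without moderate itch or pain. These counts assume that both texts use the same 1-to-10 intensity scale and that the Section 9 score applies to swelling and to pain separately; the text confirms neither. How many participants or events would be affected is unknown. The conclusion also assumes that no unseen document states which rule governs. Which threshold is clinically right is not judged here.

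**What to change.** Reconcile Section 9 with the Appendix B scripts for redness or rash, itchiness, pain and swelling, so that each sign has one recording definition and one relatedness rule, used by coaches and the coordinator alike. The sponsor and clinicians should choose the thresholds and the role of the 48-hour condition. State which text governs, and correct the appendix reference if Appendix B is the intended coach guidance.

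On the adverse event template, keep the raw 1–10 score for every complaint, including those below the recording threshold, together with the date and time of sensor removal or an entry that the sensor is still worn. Every report can then be classified the same way whatever its route. Summarise device adverse events under the single definition.

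The cost is protocol and script wording and one extra question per complaint call. If a 48-hour condition is kept, a complaint made during wear cannot be classified on that call, so a check is needed at one of the weekly coaching calls already scheduled.
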